#### **4.3.1 Consent Description**

Informed consent will take place in the preoperative holding area the day of the scheduled procedure. The investigator will perform the informed consent process by re-explaining the study in detail, providing the ICF/HIPAA, and obtaining the subject's signature.

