### **5.2 Study Design and Duration**

This a prospective, observational pilot study that aims to evaluate an Oxygenating Bite Block prototype in obese patients undergoing endoscopy. The endoscopy procedure nor the anesthesia management will change from current practices. The investigators will

hand out a short questionnaire to the patient, anesthesiologist, and endoscopist following the procedure regarding tolerability and/or feasibility of the device.

The duration of the study is about one day.

The study will be conducted on-site at Cedars-Sinai.

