### **5.3 Description of Study Procedures**

The study involves participation at a single timepoint only. The study procedures to be done are listed below.

The only data to be collected are three questionnaires. Following the procedure, the patient, anesthesiologist, and gastroenterologist will be given a short questionnaire administered in-person regarding the tolerability and feasibility of the OBB.

The following will be collected and analyzed from the patient questionnaire:

- 1) Satisfaction of sedation level during the procedure
- 2) Tolerability of the OBB
- 3) Presence of a sore throat

The following will be collected and analyzed from the anesthesiologist questionnaire:

- 1) Ease of use of the OBB
- 2) Adequacy of teeth protection
- 3) Efficacy of oxygenation of the OBB
- 4) Efficacy of oxygenation in comparison with currently available alternatives for MAC
- 5) Efficacy of ETCO2 monitoring
- 6) Potential future use of the OBB
- 7) Desaturation of patient
- 8) Professional opinion of the OBB

The following will be collected and analyzed from the gastroenterologist questionnaire:

- 1) Patient tolerability of the OBB
- 2) Potential future use of the OBB
- 3) Interference of the OBB with endoscopy performance
- 4) Professional opinion of the OBB

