## **6.0 Data Collection and Management**

### **6.1 Data Procurement**

- **Identification/Access/Abstraction**

- Members of the study team will require access to the clinical data source (e.g., electronic medical record) to identify eligible data/specimens and to conduct data abstraction or gain access to specimens.
- Separate registry or repository will identify, abstract, and/or provide specimens and/or data to the study team.
- Other:

Data will be collected directly from the patient, anesthesiologist and endoscopist using a questionnaire and no identification will be included.

- **Source(s) of Data/Specimens:**

No medical record data will be accessed as part of this research.  
All data is collected from the questionnaire for the patient, questionnaire for the anesthesiologist, and questionnaire for the gastroenterologist.

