### 8.3 Statistical Analysis Methodologies

This pilot study will obtain *response rates*. The questionnaire for the patient, questionnaire for the anesthesiologist, and questionnaire for the gastroenterologist for this research study, will be collated and reviewed by the investigator to provide the outcome data. We will use *frequencies and percentages and the similar responses will be compared across the 3 questionnaires applied*.

No statistical methods description is required given that the study does not require a sample size justification.

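### Sore throat is asked only after the procedure, so the planned percentage cannot separate new from pre-existing cases

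*Combined protocol and SAP*

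**What the plan says.** Section 5.3 gives three items for the patient questionnaire: satisfaction with sedation, tolerability of the OBB, and "Presence of a sore throat". The form is described as a "short questionnaire administered in-person regarding the tolerability and feasibility of the OBB". On timing, section 5.2 has the investigators "hand out a short questionnaire to the patient, anesthesiologist, and endoscopist following the procedure".

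Three statements close off a baseline answer:

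- Section 5.3: "The study involves participation at a single timepoint only".
- Section 5.3: "The only data to be collected are three questionnaires".
- Section 6.1: "No medical record data will be accessed as part of this research".

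Section 6.3 adds diagnosis and date of treatment as data elements, but no symptom history. Section 4.2 does not name sore throat as an exclusion; it has only a general clause on interfering conditions.

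The analysis in section 8.3 is "frequencies and percentages and the similar responses will be compared across the 3 questionnaires applied". It has no rule for separating new from existing symptoms, and none for attributing symptoms to a cause.

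There is already a contact before the procedure. Section 4.3.1 says "Informed consent will take place in the preoperative holding area the day of the scheduled procedure".

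**The concern.** As described in 5.3, the item is about presence, not onset or change. Some patients coming for upper endoscopy may already have a sore throat. If they answer truthfully afterwards, they are counted with the patients whose sore throat began during the procedure, and the reported percentage can only move upwards as a result.

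Tolerability is part of the first primary objective (section 3.0), and sore throat is the only specific symptom that patients are asked about. A reader who sees its percentage among the OBB tolerability results will tend to take it as something that happened during the study.

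The loss cannot be repaired later. Sections 6.1 and 6.4 say that the forms carry no identification and that no private identifiable information is collected, so the plan offers no route back to a patient to ask.

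**Working it through.** **The plan's own figure.** There is none to reproduce. Section 8.1 sets 10 subjects and section 8.2 claims a pilot exemption. No expected sore-throat rate, error rate or precision target is given.

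**Is a baseline available anywhere?** The possible sources, one by one:

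- Patient questionnaire: given once, after the procedure (5.2, 5.3).
- Anesthesiologist and gastroenterologist questionnaires: no sore-throat item in either list (5.3).
- Medical record: not accessed (6.1).
- Other data elements: diagnosis and date of treatment only (6.3).
- Eligibility: sore throat at entry is not a named exclusion (4.2).

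So no baseline answer is planned.

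**Size.** The rates below are assumptions, for scale only. Let p be the share of patients who arrive with a sore throat and q the share in whom the procedure produces one. Take the two as independent, and suppose that a prior sore throat is still reported afterwards.

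- Recorded rate = 1 − (1 − p)(1 − q)
- Upward shift = recorded rate − q = p(1 − q)
- Chance that at least one of 10 patients arrives with a sore throat = 1 − (1 − p)^10

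With q = 20%:

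| Assumed p | Recorded rate | Shift (points) | Chance of at least one prior case in 10 |
|---|---|---|---|
| 2% | 1 − 0.98 × 0.80 = 21.6% | 1.6 | 18.3% |
| 5% | 1 − 0.95 × 0.80 = 24.0% | 4.0 | 40.1% |
| 10% | 1 − 0.90 × 0.80 = 28.0% | 8.0 | 65.1% |
| 20% | 1 − 0.80 × 0.80 = 36.0% | 16.0 | 89.3% |

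Other values of q give the same picture. With q = 10%, p of 2%, 5% and 10% gives 11.8%, 14.5% and 19.0%. With q = 30%, it gives 31.4%, 33.5% and 37.0%.

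**Per patient.** One patient in 10 is 10 percentage points. A prior case adds the full 10 only if that patient would not also have developed a new sore throat. Otherwise it adds nothing, because the patient would have been counted anyway. Hence up to 10 points, and 8 on average when q = 20%.

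**Against sampling error.** Exact (Clopper-Pearson) 95% limits at n = 10 are 0.3% to 44.5% for 1/10, 2.5% to 55.6% for 2/10, and 6.7% to 65.3% for 3/10. Around 20%, the limits lie 20 − 2.5 = 17.5 points below and 55.6 − 20 = 35.6 points above. Even the largest shift in the table, 16 points, is smaller than either.

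**The case against.** A reader might infer that the plan counts a pre-existing sore throat as an effect of the device. The document does not support that. No section attributes sore throat to the OBB, and 8.3 plans only descriptive counts. What stands is narrower: the figure mixes old and new cases, and it appears under a heading that invites a device reading.

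It is also tempting to say that the item definitely ignores onset. The entry in 5.3 is a label for what is collected, not the wording of the question, and the questionnaire is not in the document. The item may ask about sore throat since the procedure. If so, the remedy is only to say that in 5.3.

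Three further objections have weight:

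- The shift is smaller than the sampling error, and at a prior rate of 2% there is most likely no prior case among the 10. That is true and keeps the point minor. But an interval would show imprecision, whereas nothing in the collected data would show this bias.
- No threshold, test or progression rule depends on sore throat, and the patient's tolerability rating may also capture harm. That stands too.
- A baseline answer would not isolate the OBB. An endoscope is passed through the device in every patient and there is no comparison group. This is correct, but removing pre-existing cases is a separate matter that needs no comparator.

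**Conclusion.** The point holds as a minor one: a cheap improvement. Sore throat is recorded once, afterwards, as presence, and nothing planned supplies a baseline, so new and pre-existing cases cannot be separated.

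The size is unknown from the document. Under the assumptions shown (independence, 20% new onset, 2% to 20% prior), the recorded rate would be about 22% to 36% in place of 20%. The direction is always upwards.

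The conclusion depends on the questionnaire matching its description in 5.3. It does not extend to a claim that the plan blames the device for prior symptoms, or that the bias would dominate what 10 patients can show.

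**What to change.** **Section 5.3.** Add one yes/no sore-throat question in the holding area, right after consent. Record it on the same unnamed patient form that is completed after the procedure. The plan describes no study number, so using one form links the two answers without adding an identifier. Amend the single-timepoint wording to match. If the existing question already asks about onset, say so here.

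**Section 8.3.** Report new sore throat, meaning absent before and present after, with the pre-procedure count and the overall post-procedure count beside it. State the denominator. Among patients free of sore throat beforehand, the figure recovers the assumed 20%; over all patients, with 10% prior, it would be 0.90 × 0.20 = 18%. Two yes/no answers cannot show worsening, so report worsening only if the same severity scale is used both times. State that the figure reflects the OBB and endoscope together and cannot be assigned to the OBB alone.

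**Cost.** One extra question at a contact that already takes place, a line each in 5.3 and 8.3, and a form that must stay with the patient's study papers until after the procedure. The sample size does not change. Adding an onset question to the post-procedure form would avoid the earlier entry, but it relies on recall after sedation.

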## **6.0 Data Collection and Management**

### **6.1 Data Procurement**

- **Identification/Access/Abstraction**

- Members of the study team will require access to the clinical data source (e.g., electronic medical record) to identify eligible data/specimens and to conduct data abstraction or gain access to specimens.
- Separate registry or repository will identify, abstract, and/or provide specimens and/or data to the study team.
- Other:

Data will be collected directly from the patient, anesthesiologist and endoscopist using a questionnaire and no identification will be included.

- **Source(s) of Data/Specimens:**

No medical record data will be accessed as part of this research.  
All data is collected from the questionnaire for the patient, questionnaire for the anesthesiologist, and questionnaire for the gastroenterologist.

## 6.2 Time Period of Data under Review

- Data will be collected from/at the following timepoints: Same day of the scheduled procedure.
- Information will be stored in a locked office of the investigators and maintained for a minimum of two years after the completion of the study.

## 6.3 Data Elements

The following data points will be collected:

- Diagnosis
- Date of treatment
- Questionaries responses.

The information to be accessed and reviewed is that which is minimally necessary to achieve the goals of this research.

HIPAA Identifiers
 Diagnosis
 Date of treatment

## 6.4 Confidentiality and Security of Data

- **Retention/Destruction of Study Materials:** Study data- questionnaires will be kept and/or destroyed according to applicable policy.
- **Limited Access:** No private identifiable information will be collected.

 Clinical records can only be accessed by study team members who are listed on the CS-IRB application and are IRB Certified.

- **Storage of Physical Records:** Physical records will be maintained for this study at a secure location where access is limited to approved personnel. The records will not be removed from Cedars-Sinai premises.

## 7.0 Data and Safety Monitoring

### 7.1 Data and Safety Monitoring Plan

The study will be monitored by the PI to ensure appropriate study conduct, including obtaining proper access to data/specimens, compliance with the HIPAA Privacy Rule, compliance with Cedars-Sinai policy, and adhering to the plans outlined in the protocol for all study procedures, abstracting and recording data, data and/or specimen security and maintenance, and data accuracy and integrity. Any adverse events, deviations, protocol exception requests, potential unanticipated problems involving risks to subjects or others, or other events will be submitted to the IRB in accordance with [IRB reporting policy](#). All study procedures will be conducted in accordance with standard clinical practice.

## 8.0 Sample Size and Statistical Considerations

### 8.1 Sample Size

This is a single on-site study at Cedars-Sinai. The sample size of the study is 10 subjects.

### 8.2 Statistical Sample Size Justification

A statistical sample size is not required because this study involves:

- A pilot study with at most 20 subjects

### 8.3 Statistical Analysis Methodologies

This pilot study will obtain *response rates*. The questionnaire for the patient, questionnaire for the anesthesiologist, and questionnaire for the gastroenterologist for this research study, will be collated and reviewed by the investigator to provide the outcome data. We will use *frequencies and percentages and the similar responses will be compared across the 3 questionnaires applied*.

No statistical methods description is required given that the study does not require a sample size justification.

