### 3.0 Study Purpose and Objectives

The primary objectives of this study are:

- 1) To evaluate the tolerability and efficacy of the Oxygenating Bite Block during sedation for endoscopic procedures.
- 2) To evaluate the Oxygenating Bite Block from the endoscopist and anesthesiologist perspective. These professionals will be part of the study team.

The secondary objectives of this study are:

- 1) To collect preliminary answers regarding the physician and patient tolerability and feasibility of the OBB through questionnaires.

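### Adverse events sent to the IRB have no route into the tolerability result unless a same-day questionnaire item happens to capture them

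*Combined protocol and SAP*

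**What the plan says.** Section 3.0 gives the first primary objective as "To evaluate the tolerability and efficacy of the Oxygenating Bite Block during sedation for endoscopic procedures". Sections 2.0 and 5.2 describe the device as an investigational prototype without 510(k) clearance.

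The outcome data come from one place. Section 5.3 states: "The only data to be collected are three questionnaires". Section 6.1 repeats that all data come from the questionnaires and adds: "No medical record data will be accessed as part of this research". Section 8.3 says that the questionnaires "will be collated and reviewed by the investigator to provide the outcome data" and that they are summarised as frequencies and percentages. Section 6.3 adds only the diagnosis and the treatment date.

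Collection is limited to one time point, given in section 6.2 as "Same day of the scheduled procedure". No later contact is described.

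Safety events follow a different route. Section 7.1 covers "Any adverse events, deviations, protocol exception requests, potential unanticipated problems involving risks to subjects or others" and sends these to the IRB. Neither that section nor section 8.3 says that they are tabulated or used in the results.

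**The concern.** Tolerability is normally judged from what patients and operators report together with the adverse events that occurred. Here the two are kept apart. The investigators may hold a report of a device-related event in the IRB file, while the analysis as written draws only on questionnaire answers.

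The questionnaires name two specific harms: sore throat (patient form) and desaturation (anesthesiologist form). The other relevant items, such as tolerability, teeth protection and interference with the endoscopy, are ratings or opinions and not records of events. An injury to the mouth, lip or tooth has no field of its own. An event that comes to light after the forms are filled in has no route at all.

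What is at stake is the completeness of a primary result. A small pilot of an uncleared device informs later decisions about that device, and a reader of its tolerability summary will assume that known adverse events were taken into account.

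**Working it through.** **The plan's own figure.** Section 8.1 states: "The sample size of the study is 10 subjects". Section 8.2 gives no calculation ("A statistical sample size is not required because this study involves" a small pilot), so there is nothing to reproduce, and no stated figure depends on this point.

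**Tracing events through the plan** (sections 5.3, 6.2, 7.1 and 8.3 read together):

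| Type of event | On a form? | Reported under 7.1? | In the 8.3 result? |
|---|---|---|---|
| Sore throat present when the form is completed | Yes, patient | Possibly | Yes |
| Desaturation during the procedure | Yes, anesthesiologist | Possibly | Yes |
| Mouth, lip or tooth injury seen on the day | No item of its own; may colour a rating | Yes, if an adverse event | Not as an event |
| Any event that becomes known after the forms | No | Yes, if it reaches the investigators | No |

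The last two rows are the gap.

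**Size at n = 10.** One affected patient is 1/10 = 10 percentage points. Exact (Clopper-Pearson) two-sided 95% intervals for x patients with an event:

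- x = 0: 0%. The upper limit is 1 − 0.025^(1/10) = 30.8%.
- x = 1: 10%. The lower limit is 1 − 0.975^(1/10) = 0.3%; the upper limit is the 97.5% point of Beta(2, 9) = 44.5%.
- x = 2: 20%, interval 2.5% to 55.6%.

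Leaving out one patient's event thus changes the estimate from 10% to 0% and the upper limit from 44.5% to 30.8%.

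**How likely is at least one such event?** The documents give no rate, so a range is assumed for p, the true per-patient rate of an event that the forms do not capture. The chance of at least one in 10 patients is 1 − (1 − p)^10:

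| Assumed p | Chance of at least one |
|---|---|
| 5% | 1 − 0.95^10 = 40% |
| 10% | 1 − 0.90^10 = 65% |
| 20% | 1 − 0.80^10 = 89% |

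At an assumed 1% it is 1 − 0.99^10 = 10%. The conclusion about the text does not depend on p; p affects only how often the gap would matter.

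**The case against.** The strongest reply is that the forms already cover much of what can be foreseen. Two clinicians see the procedure and both complete a form. Between them and the patient, the forms ask about tolerability, sore throat, desaturation, teeth protection, interference and overall opinion. A serious intra-procedural problem would probably colour at least one answer. This stands, and it limits the point to events outside those items or after the forms. It does not close the gap, because a rating that has been influenced by an injury does not report the injury.

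A second reply is that section 8.3 only explains how questionnaires are summarised, that safety sits in its own section, and that nothing forbids reporting the two together. The word *only* in section 5.3 is also not literal, since section 6.3 lists two further data elements. This is fair: the plan does not prohibit using the events. But neither added element is an adverse event, and a reader following the text would have no instruction to use the IRB reports.

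A third reply is that this is a descriptive 10-patient pilot with IRB reporting in place. That limits the severity. IRB reporting protects subjects; it does not put an event into the published tolerability result.

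**Conclusion.** The point holds in a limited form. As written, an adverse event that no questionnaire item captures, or that becomes known after the forms are completed, can be known to the investigators and still be absent from a primary-objective result. Each affected patient is 10 percentage points. The probabilities in the working rest on assumed rates. No sample size, test or decision rule is wrong because of this, and IRB safety reporting is unaffected. It is a reporting gap that should be closed.

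Stronger readings are tempting but not supported:

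- A reader might infer that adverse events never reach the tolerability result. Same-day sore throat and desaturation do, through the forms.
- A reader might infer that the study could announce full tolerability in every patient despite a known event. The plan defines no yes/no tolerability endpoint, scale or threshold, so no such output is specified.
- A reader might infer that the sore-throat percentage is materially too low because symptoms appear later. The documents do not say how long after the procedure the form is completed and give no onset times, so the size of any shortfall is unknown. What can be said is that the item measures same-day sore throat and should be described that way.

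**What to change.** Add to section 8.3: *All adverse events, and any device-related deviations, submitted under section 7.1 will be listed at study level, without linkage to individual questionnaires, beside the questionnaire tolerability results, and will be considered in the conclusion on tolerability. If there are none, this will be stated.* Also label the sore-throat percentage *on the day of the procedure*.

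The listing is kept unlinked because section 6.1 has no identification on the forms and section 6.4 rules out private identifiable information; matching events to forms would need a study code that the protocol does not describe. The single-time-point design does not have to change.

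The cost is two short edits and a brief extra listing, with no new data and no added patient burden. The tolerability statement may become less favourable if events occurred. There are two limits: without linkage, the listing cannot show whether a patient with an event also rated the device poorly, and it will contain later events only if they happen to reach the investigators.

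### Section 8.3 declares a methods description unnecessary, leaving a comparison between questionnaires with no method or stated link between a patient's forms, and percentages from 10 patients without intervals

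*Combined protocol and SAP*

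**What the plan says.** Section 8.3 says the investigator will collate the three questionnaires and summarise them as frequencies and percentages, and that "the similar responses will be compared across the 3 questionnaires applied". It ends: "No statistical methods description is required given that the study does not require a sample size justification". Section 8.1 sets 10 subjects, and Section 8.2 waives a sample size calculation because this is a small pilot.

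The first primary objective in Section 3.0 is: "To evaluate the tolerability and efficacy of the Oxygenating Bite Block during sedation for endoscopic procedures". Section 5.2 describes an observational pilot, with no control group. Section 5.3 makes the three questionnaires the only data. The anesthesiologist form includes "Desaturation of patient" and "Efficacy of oxygenation in comparison with currently available alternatives for MAC"; the gastroenterologist form includes "Patient tolerability of the OBB".

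On identification, Section 6.1 says data are collected "using a questionnaire and no identification will be included". Section 6.3 lists diagnosis and "Date of treatment" as data elements but does not say that either is used to match forms. No study number or form code is mentioned anywhere.

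**The concern.** How many patients to enrol and how to summarise their answers are separate questions. Waiving the first is acceptable for a 10-patient pilot; it does not remove the need to answer the second. Section 8.3 announces an analysis and then declines to describe it. Two consequences follow.

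- **The comparison.** Nothing says which items count as similar, whether they are compared patient by patient or as totals, or what measure is reported. If the forms carry nothing that ties them to one procedure, only totals can be compared. Equal totals do not show that the patient and the gastroenterologist agreed about the same procedure. A link not recorded at collection may not be recoverable later, so this has to be settled before the first form is completed.
- **The percentages.** With 10 uncontrolled patients and an objective worded as efficacy, a bare 0% or 100% can be read as a finding about the device although it fits a wide range of true rates.

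**Working it through.** **The plan's own figure.** The 10 subjects cannot be re-derived, because no error rate, effect or precision target is given. Section 8.2 openly waives this, and it is not the defect.

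**Step 1: which items can be compared.** Section 5.3 lists 3 patient + 8 anesthesiologist + 4 gastroenterologist = 15 items. Topics on more than one form:

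| Topic | Patient | Anesthesiologist | Gastroenterologist |
|---|---|---|---|
| Tolerability | yes | no | yes |
| Potential future use | no | yes | yes |
| Professional opinion | no | yes | yes |

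No topic is on all three. Only tolerability is a judgement about the individual patient's procedure made by two people. Future use and professional opinion are largely attitudes to the device.

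**Step 2: what unlinked totals can show.** Assume tolerability is yes/no and 10 forms of each kind are returned. Let a and b be the numbers of favourable answers on the patient and gastroenterologist forms, and k the number of patients for whom both are favourable. Then k runs from max(0, a + b − 10) to min(a, b), and the number agreeing is k + (10 − a − b + k) = 2k + 10 − a − b.

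| a = b | k | Patients in agreement |
|---|---|---|
| 8 | 6 to 8 | 12 − 6 = 6 up to 16 − 6 = 10 |
| 7 | 4 to 7 | 8 − 4 = 4 up to 14 − 4 = 10 |
| 5 | 0 to 5 | 0 up to 10 |

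Identical percentages on the two forms are therefore compatible with full agreement and with a good deal of disagreement.

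**Step 3: uncertainty in a single percentage.** Exact (Clopper-Pearson) two-sided 95% intervals, for a yes/no item answered by all 10; the 95% level is an assumption.

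- 0/10: upper limit 1 − 0.025^(1/10) = 30.8%, so 0 to 30.8%.
- 8/10: from beta quantiles, 44.4 to 97.5%.
- 10/10: lower limit 0.025^(1/10) = 69.2%, so 69.2 to 100%.

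For illustration, Section 2.0 gives hypoxemia in 11 to 50% of procedures. If the true desaturation rate were 11%, no event in 10 would occur with probability 0.89^10 = 31.2%; at 50% it would be 0.5^10 = 0.1%. The desaturation item has no stated definition and may not match that background figure, so this shows scale only.

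**Step 4: would a test help?** No. If all d discordant pairs go one way, exact McNemar gives p = 2 × 0.5^d: 0.063 at d = 5 and 0.031 at d = 6. At least 6 of 10 pairs would have to disagree, all in one direction.

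**The case against.** The strongest reply is that this is a pilot with no hypothesis, success threshold or go/no-go rule. Section 8.3 does name frequencies and percentages. Anyone given x/10 can compute an interval afterwards. The comparison can be read as totals side by side, which needs no link. With 10 patients and forms handed out in person, the team may well know which forms belong together.

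Much of this stands, and it rules out several stronger readings.

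- A reader might infer that there is no analysis method at all. There is one, though thin; the fault is the closing sentence and what it leaves open.
- A reader might infer that the forms cannot be linked. The documents do not show that. The questionnaires are not in the supplied text, so a printed form number cannot be excluded. The ban on identification need not bar a neutral study number, given that Section 6.4 is concerned with private identifiable information. Section 6.1 says all data come from the questionnaires, so treatment date and diagnosis would seem to be on at least one form. They are not said to be on all three, and a date would not separate two study patients treated on one day.
- A reader might infer that a within-patient analysis was promised and cannot be delivered. Section 8.3 does not say which comparison is meant.
- A reader might infer that repeated forms from a few physicians distort the results. The number of physicians is not stated, so this remains unknown.

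What the reply does not remove: side-by-side totals are the weaker reading of the comparison and leave agreement unanswered. Intervals can be added later; a missing link may not be.

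**Conclusion.** The point holds in this limited form. The reason given for omitting a methods description is a non sequitur. The planned comparison has no defined items, pairing or measure, and the text provides no way to match a patient's forms. Followed as written, it may yield only totals; 8/10 on each of two forms leaves within-patient agreement anywhere from 6/10 to 10/10. That range assumes a yes/no tolerability item and complete returns. Reporting bare percentages also conceals intervals as wide as 0 to 30.8% or 69.2 to 100% under an objective worded as efficacy. Those intervals apply only to items recorded as yes/no, which the supplied text does not confirm.

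This does not invalidate the pilot, and the absence of a power calculation is not a fault. It should be corrected before data collection, because the link depends on what is written on the forms at that time.

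**What to change.** 1. Delete the last sentence of Section 8.3.
2. Put a non-identifying study number on all three forms, and reconcile the no-identification statement in Section 6.1 with it. If the forms already carry a number, one sentence saying so is enough.
3. Compare patient and gastroenterologist tolerability within patient, as a cross-table with the count agreeing and no test. Show future use and professional opinion only as side-by-side distributions for the two physician groups, and report the number of distinct anesthesiologists and gastroenterologists.
4. Report every item as x/n, with n the forms that answer it. Where recorded as yes/no, give an exact 95% interval for sedation satisfaction, the patient's own tolerability rating, sore throat and desaturation. Give the full distribution for graded items.
5. In Section 3.0, describe the efficacy part as preliminary, questionnaire-based ratings of oxygenation, and say that it is not a test of efficacy.

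The cost is one code field per form and a few lines in Sections 3.0, 6.1 and 8.3, with no extra patients or visits. The downside is that results will look less certain. The desaturation interval will be only as clear as the wording of that item, for which the documents give no definition.
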